Description of Study Intervention:	
This is a case series, in which burn patients meeting all of the inclusion criteria and none of the exclusion criteria will receive Hyalomatrix® Wound Device as a matrix for their wound, in conjunction with the standard-of-care for managing these types of wounds. The study will be divided into two phases. Phase I will entail intervention with the Hyalomatrix® Wound Device and will continue until one of the following occurs, (1) sufficient granulation has occurred and the patient can receive an STSG and proceed to Phase II, (2) the patient's physician determines an STSG is no longer necessary, or (3) two applications with the Hyalomatrix® Wound Device occur and no STSG is approved. Phase II will begin following the STSG procedure. In this phase the wound will be monitored and proportion of STSG take will be evaluated, but no application of the Hyalomatrix® Wound Device will take place. This phase will continue for 28 days or if the physician deems the patient no longer needs regular care to monitor the wound, whichever occurs earlier.

Participant Duration:	
Participant duration will begin upon obtaining informed consent and will end when one of the following occurs:
 
(1) The patient completes Phase II,(2) the patient's physician determines an STSG is no longer necessary,(3) the patient is unwilling or clinically inappropriate, per determination by the Investigator, to receive a second application of Hyalomatrix® Wound Device or STSG. The silicone backing should be removed at 21 days but the decision to reapply the Hyalomatrix® Wound Device or schedule the STSG may happen up to three days thereafter,(4) the patient is not ready to receive an STSG after two applications with the Hyalomatrix® Wound Device. The silicone backing should be removed 21 days after the second application of Hyalomatrix® Wound Device but the decision to schedule the STSG may happen up to three days thereafter,,(5) the patient develops an infection of the target wound at any time,(6) the patient needs NPWT of the target wound after application of the Hyalomatrix® Wound Device.

A clinical evaluation of an esterified hyaluronic acid matrix on preparing wounds in burn patients for split-thickness skin grafting

MED-2018-DIV31-006

V2.0

CONFIDENTIAL

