Overall time will be variable depending on the patient's wound and condition; however, typical time for a wound to be ready for grafting following the use of the Hyalomatrix® Wound Device is 14-21 days after initial matrix application. Time to heal after STSG application is typically two weeks, but the patient will remain in the Phase II portion of the study while the wound is still open, up to a maximum period of 28 days post STSG.

A clinical evaluation of an esterified hyaluronic acid matrix on preparing wounds in burn patients for split-thickness skin grafting

MED-2018-DIV31-006

V2.0

CONFIDENTIAL

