3. OBJECTIVES AND ENDPOINTS

OBJECTIVES	ENDPOINTS	JUSTIFICATION FOR ENDPOINTS
Primary		
Evaluate the capability of the device to prepare post-escharectomy wounds in burn patients to receive an STSG.	Number of days from initial application of the device to approval of wound to receive an STSG.	Marker of wound healing progress
Secondary		

A clinical evaluation of an esterified hyaluronic acid matrix on preparing wounds in burn patients for split-thickness skin grafting

MED-2018-DIV31-006

V2.0

CONFIDENTIAL

1. Evaluate clinical outcomes of burn patients 2. Health outcomes	(1a) Change in wound volume from the time prior to application of the device to the time before the application of STSG and after STSG (1b) Length-of-stay at inpatient unit (1c) Patient pain rating (1d) Proportion of STSG take for the wound at 28 days, per clinician judgement (1e) Proportion of patients who develop an infection of the target wound at any time, per confirmation with culture (2a) Length-of-stay as inpatient (2b) Type of care setting where patient is discharged	Common clinical endpoints to measure outcomes in wound management. Common analysis to determine cost-effectiveness of device usage.
----------------------------------------------------------------------	-------------------------------------------------------------------------------------------------------------------------------------------------------------------------------------------------------------------------------------------------------------------------------------------------------------------------------------------------------------------------------------------------------------------------------------------------------------------------------------------------------------------	--------------------------------------------------------------------------------------------------------------------------------------------

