8.2. Populations for Analyses

An evaluable population will be used for all analyses, with the definition of evaluable depending on the Phase of the study. For Phase I, all patients with an initial visit and a final interim visit resulting in resolution of Phase I will be included. In Phase II, patients with data from any interim visits who also complete Phase II to resolution will be included in analyses for Phase II.

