8.3. Statistical Analysis

Descriptive statistics, including measures of central tendency (mean or median), measures of variation (standard deviations, coefficients of variation) and 95% confidence intervals and interquartile ranges, as appropriate, for the data distribution will be calculated for all endpoints. Demographic and baseline characteristics will be assessed as above and additional statistical analyses may be conducted in an exploratory fashion, as appropriate, for the data distribution.

- Time (in days) from initial application of wound matrix to approval of wound to receive an STSG.
- Change in wound volume from the time prior to application of the wound matrix to the time before the application of STSG and after STSG
- Length-of-stay as an inpatient

A clinical evaluation of an esterified hyaluronic acid matrix on preparing wounds in burn patients for split-thickness skin grafting

MED-2018-DIV31-006

V2.0

CONFIDENTIAL

- Patient pain ratings
- Proportion of STSG take, per clinician judgement, for the wound at 28 days
- Proportion of patients who develop an infection of the target wound at any time, per confirmation with culture
- Type of care setting where patient is discharged

Healthcare economics outcomes will be explored by combining length-of-stay data (both phases) and the type of care setting where the participant is discharged, with standard costs, reimbursement codes and other relevant health economics economic factors.

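### On its natural reading, the completion condition in section 8.2 leaves grafted patients who exit for infection or NPWT out of the graft-take endpoint (1d)

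*Combined protocol and SAP*

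**What the plan says.** Section 8.2 sets the general rule: "An evaluable population will be used for all analyses". For the post-graft part it adds that "patients with data from any interim visits who also complete Phase II to resolution will be included in analyses for Phase II". The documents define no all-grafted or all-treated set and do not say what counts as resolution.

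Endpoint 1d appears in section 3 as "1d) Proportion of STSG take for the wound at 28 days, per clinician judgement" and in section 8.3 as "Proportion of STSG take, per clinician judgement, for the wound at 28 days". Endpoint 1e is "Proportion of patients who develop an infection of the target wound at any time, per confirmation with culture"; neither section assigns it to an analysis set.

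On timing, the Synopsis states "Phase II will begin following the STSG procedure" and "This phase will continue for 28 days or if the physician deems the patient no longer needs regular care to monitor the wound". It also states "Time to heal after STSG application is typically two weeks", and keeps patients in the phase while the wound remains open, up to 28 days after the graft. Section 6.2.1 has the investigator judge percentage take at each Phase II visit. Section 8.1 describes a case series of 20 patients with no hypothesis testing.

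**The concern.** Infection of the target wound and need for NPWT both end participation, and both can occur after grafting. If such patients have not completed Phase II, the 1d summary and its 95% confidence interval describe only grafted patients who avoided those two events. The take already recorded for the others would go unused. If their take is worse, the reported take looks better than the experience of everyone grafted. In a study whose whole output is descriptive estimates and intervals, the denominator largely decides how the graft result can be read.

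**Working it through.** **Step 1: what completing Phase II means.** The documents, side by side:

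- Synopsis (Description of Study Intervention) and section 6.2.1: Phase II has two ends, 28 days or regular care no longer being needed.
- Synopsis (Participant Duration) and section 4.2: completing Phase II is one item in a list of ways participation ends. Target-wound infection and need for NPWT are separate items. Infection applies at any time and NPWT at any point after device application, so both cover the post-graft period.
- Section 6.1.2.5: an infected patient's participation is terminated. Section 4.1: a patient given NPWT is discontinued.

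A grafted patient who leaves by either route has therefore not completed Phase II in the protocol's own terms, and section 8.2 leaves that patient out of Phase II analyses. A patient released early because regular care is no longer needed has completed the phase and stays in.

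**Step 2: effect on 1d.** There is no planned figure to reproduce: the documents give no number grafted, exit rate or take value. Let n be the number grafted, k the infection or NPWT exits, C the completers' mean take and E the exits' mean take.

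- Mean over all grafted = ((n − k)·C + k·E) / n
- Overstatement = C − that mean = (k/n)·(C − E)

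With n = 16 (assumed), in percentage points:

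| Exits k | Gap 10 | Gap 30 | Gap 50 |
|---|---|---|---|
| 1 | 10/16 = 0.6 | 30/16 = 1.9 | 50/16 = 3.1 |
| 2 | 20/16 = 1.3 | 60/16 = 3.8 | 100/16 = 6.3 |
| 3 | 30/16 = 1.9 | 90/16 = 5.6 | 150/16 = 9.4 |

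If all 20 are grafted, one exit gives 10/20 = 0.5 to 50/20 = 2.5 points, and three give 30/20 = 1.5 to 150/20 = 7.5. The result is 0 if k = 0 or C = E. These are illustrations, not bounds.

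**Step 3: endpoint 1e.** A grafted patient has had an initial visit and a final Phase I visit that led to grafting, so would ordinarily already be in the Phase I set. A post-graft infection is lost only if 1e is summarised in the Phase II set, and nothing in the documents puts it there. An all-grafted denominator would not suit 1e either, because it omits infections before grafting.

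**Step 4: the 28-day value.** 1d is fixed at 28 days, but Phase II may end sooner and no rule gives the value for a patient released early. Section 8.2 admits data from any interim visit, which fits a last-value reading. Under that reading this gap has no effect on the estimate.

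**The case against.** **Resolution might include any exit.** It is undefined, so the text does not strictly exclude this. Section 8.2 would then remove only patients who withdraw or are lost. But the Synopsis and section 4.2 list completion apart from infection and NPWT, so this is the less natural reading. Two readings that give different denominators should in any case be settled in writing.

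**The exits would not vanish from the report.** Infection is recorded as an expected adverse event (section 6.1.2.5), and returns to the operating room for the target wound are captured (section 6.2.1). That stands as mitigation, but it does not put those patients' take values back into 1d.

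**The set does not select on take.** This stands. A patient with poor take but no infection or NPWT remains in follow-up and is counted. A reader might infer that the plan keeps only successful grafts. It does not: it omits two specific exit routes, and any bias depends on take being lower in those exits.

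**Other stronger readings.** A reader might infer that 1e is bound to show no post-graft infections. That holds only if 1e uses the Phase II set, which no section says. A reader might also infer that the 28-day origin is contradictory, because the section 1.2 column heading counts from Phase I completion and section 6.1.3 records approval and planned procedure dates separately. The Synopsis and section 6.2.1 tie Phase II to the graft procedure, so this is a column label to tidy.

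**Conclusion.** The point holds for 1d, as a minor one. On the natural reading of section 8.2, grafted patients who exit for target-wound infection or NPWT are left out of the take summary. The reading itself is well supported; the size of the effect is unknown. It rests on an assumed number grafted (16, with 20 as the alternative), an assumed count of exits, and the unstated premise that exits have lower take. Within the range shown with 16 grafted, the overstatement runs from 0.6 to 9.4 points. No test, error rate or decision rule is affected.

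For 1e, what the documents support is a missing denominator, not a demonstrated loss of infections. The missing rule for the 28-day value and the schedule label are clarifications to make in the same edit.

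**What to change.** - **Section 8.2:** for 1d, replace the completion condition with all patients who receive an STSG.
- **Sections 3 and 8.3:** define 1d as percentage take at the last Phase II assessment up to and including the Day-28 visit (±2 days), counted from the graft procedure. Patients released early contribute their final assessment.
- **Reporting:** give the number of infection and NPWT exits and their last take values, and state how many had no take assessment. Add one sensitivity summary that sets all of these exits to 0% take, as a bound.
- **Endpoint 1e:** report it on all patients who received the device, so that infections before and after grafting both count.
- **Section 1.2:** relabel the Phase II column to count from the graft procedure. In the same edit, align the infection-evaluation row, marked only under Phase I, with section 6.1.2.5, which requires evaluation at all visits.

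The cost is wording. Take is already judged at each Phase II visit and infection is already evaluated throughout participation, so no new data item and no change to patient care are needed. The downsides are that assessment times will differ between patients, and that an exit's last take value may precede later graft change or not exist. The 0% summary bounds that uncertainty but does not remove it.

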8.3. Statistical Analysis

Descriptive statistics, including measures of central tendency (mean or median), measures of variation (standard deviations, coefficients of variation) and 95% confidence intervals and interquartile ranges, as appropriate, for the data distribution will be calculated for all endpoints. Demographic and baseline characteristics will be assessed as above and additional statistical analyses may be conducted in an exploratory fashion, as appropriate, for the data distribution.

- Time (in days) from initial application of wound matrix to approval of wound to receive an STSG.
- Change in wound volume from the time prior to application of the wound matrix to the time before the application of STSG and after STSG
- Length-of-stay as an inpatient

A clinical evaluation of an esterified hyaluronic acid matrix on preparing wounds in burn patients for split-thickness skin grafting

MED-2018-DIV31-006

V2.0

CONFIDENTIAL

- Patient pain ratings
- Proportion of STSG take, per clinician judgement, for the wound at 28 days
- Proportion of patients who develop an infection of the target wound at any time, per confirmation with culture
- Type of care setting where patient is discharged

Healthcare economics outcomes will be explored by combining length-of-stay data (both phases) and the type of care setting where the participant is discharged, with standard costs, reimbursement codes and other relevant health economics economic factors.

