4. STUDY DESIGN

4.1. Overall Design

This study is a multi-site, open-label case series collecting data on the clinical use of an esterified hyaluronic acid wound matrix in preparing post-escharectomy wounds in burn patients for STSGs. The study will be split into two phases. Phase I will include use of the device on the wound, with the intent of measuring how quickly the wound becomes prepared for an STSG. Phase II will occur after the STSG is placed; in this phase, the device will not be applied. Rather, the key assessment will be how well the wound is receiving the STSG. The Schedule of Activities in Section 1.2 describes the timing and sequencing of the events and phases.

In addition to the use of the wound device, physicians will provide the standard of care per their facility. However, in order to avoid confounding any conclusions attributable to the wound matrix, negative pressure wound therapy (NPWT) of the target wound will not occur during the study. Patients having NPWT on the target wound when they are screened may be included in the study (provided they meet all the inclusion criteria and none of the exclusion criteria), except when NPWT is not or cannot be discontinued after application of the device. The potential use of NPWT on the target wound, after application of the device, on a patient is listed below as an exclusion criterion. During the course of the study, if a physician determines that a patient could benefit from NPWT on the target wound, the physician can implement this therapy, and the patient will be discontinued from the study.

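### Days to STSG approval describe only approved patients; the plan does not prespecify how many treated patients reach approval or how other Phase I exits are reported

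*Combined protocol and SAP*

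**What the plan says.** Section 3 gives the primary objective: "Evaluate the capability of the device to prepare post-escharectomy wounds in burn patients to receive an STSG". The endpoint is the number of days from first application to approval, which Section 8.3 lists for analysis as "Time (in days) from initial application of wound matrix to approval of wound to receive an STSG". Section 4.1 describes Phase I as conducted "with the intent of measuring how quickly the wound becomes prepared for an STSG".

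Section 8.3 plans "Descriptive statistics, including measures of central tendency (mean or median"), with standard deviations, coefficients of variation, 95% confidence intervals and interquartile ranges as appropriate. It names no time-to-event method.

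The Phase I population in Section 8.2 is evaluable patients: "all patients with an initial visit and a final interim visit resulting in resolution of Phase I will be included". Resolution is not defined there. The Synopsis (Description of Study Intervention) lists three ways Phase I can end: the patient can receive an STSG, an STSG is no longer needed, or two applications pass without approval. Section 4.2 adds endings of participation for infection, for NPWT, and for patients unwilling or clinically unsuitable to have a second application or the graft. Section 4.1 repeats the NPWT rule: "the physician can implement this therapy, and the patient will be discontinued from the study".

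Of these exits, only infection has a planned summary: "Proportion of patients who develop an infection of the target wound at any time, per confirmation with culture". Section 8.3 also says that "additional statistical analyses may be conducted in an exploratory fashion".

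**The concern.** A patient who is never approved has no number of days to approval. The plan assigns such a patient no value, no censoring time and no competing-event status. A mean or median can then be taken only over approved patients, whoever else is in the evaluable set.

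Speed among approved wounds is a legitimate thing to measure. It is a different quantity from the share of treated wounds that became ready, and the objective is worded as capability. A reader shown only the planned summary could not tell a device that prepared every wound from one that prepared half of them equally fast. The n of the summary would reveal this only if it were reported against the number treated.

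**Working it through.** **Step 1: which exits have no primary value.** Setting the Synopsis, 4.1, 4.2, 6.1.2.5 and 6.1.3 beside the endpoint definition:

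- No approval after two applications: never has a value. On the Synopsis list it plausibly counts as resolution of Phase I, so the patient may be evaluable and still contribute no time.
- STSG no longer necessary: ends Phase I without an approval date. This is a favourable outcome.
- Infection, NPWT, unwilling or clinically unsuitable: no value if the exit comes before approval. If it comes after approval, the value exists. Section 8.2 does not say whether the pre-approval cases count as resolution.

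**Step 2: is there a figure to reproduce?** No. Section 8.1 sets 20 patients as usual for a case series, with no power calculation, and no section gives a non-approval rate.

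**Step 3: illustration.** From the documents: 20 treated; visits at Days 14, 21, 35 and 42. Assumed: all approval counts. Formulas: mean = sum of days / n approved; 95% CI = mean ± t(0.975, n − 1) × SD/√n; Clopper-Pearson interval for x/20.

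| Assumed pattern | Approvals at Days 14, 21, 35, 42 | Mean (95% CI) | SD | Median (IQR) | Approved / treated (exact 95% CI) |
|---|---|---|---|---|---|
| A. All approved | 6, 10, 2, 2 | 448/20 = 22.4 (18.2–26.6) | 8.97 | 21 (14–21) | 20/20 = 100% (83.2–100) |
| B. Four exit, near-proportional | 5, 8, 2, 1 | 350/16 = 21.9 (17.4–26.4) | 8.43 | 21 (14–21) | 16/20 = 80% (56.3–94.3) |
| C. Four slowest exit | 6, 10, 0, 0 | 294/16 = 18.4 (16.5–20.2) | 3.50 | 21 (14–21) | 16/20 = 80% (56.3–94.3) |
| D. Four faster wounds exit | 4, 8, 2, 2 | 378/16 = 23.6 (18.6–28.7) | 9.52 | 21 (17.5–28) | 16/20 = 80% (56.3–94.3) |
| E. Ten exit (extreme) | 3, 5, 1, 1 | 224/10 = 22.4 (15.8–29.0) | 9.22 | 21 (14–21) | 10/20 = 50% (27.2–72.8) |

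Example for A: t = 2.093, half-width 2.093 × 8.97/√20 = 4.2.

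A and E share a mean and a median although approval differs by 50 percentage points. C looks faster and more precise than A because four patients were not approved. D moves the other way. The common median of 21 follows from the counts chosen.

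The table uses visit-day labels. The Schedule of Activities puts application on Day 1, so if elapsed days are counted from Day 1, every mean, median, quartile and limit for days falls by one. Differences, SDs and proportions do not change.

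**Step 4: why not a fixed-day cut for the proportion.** The Day 21 visit may fall on Days 19–23 (± two days), and the decision may come up to three days after day 21 (21 + 3 = 24). If 4 of the 10 Day 21 approvals in pattern A were dated Days 22–24 (assumed), a hard Day 21 cut would give 12/20 = 60% (36.1–80.9). Counting by application number gives 16/20 = 80% (56.3–94.3). With both decision periods Phase I can run to 21 + 3 + 21 + 3 = 48 days before the visit window, so a hard Day 42 cut has the same problem.

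**The case against.** This is a 20-patient, open-label descriptive case series. Section 4.1 says that Phase I measures speed, and days to approval answers that. Approval dates are noted on the CRF (Section 6.1.3), so the proportion approved could be worked out later, and exploratory analyses are allowed. Retention in Phase I is expected not to be an issue (Section 5.3), and the Schedule of Activities expects most patients to finish by 21 days. The exit patterns above are invented. In three of the four patterns with exits the mean stays within 1.3 days of 22.4, and in the fourth its interval still overlaps that of pattern A.

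Most of this stands as a limit on the size of the point. What is missing is prespecification; the information itself is largely recoverable. It does not remove the gap: retention is not approval, an optional exploratory analysis is not a commitment, and a stable mean alongside a falling proportion is exactly what the reader cannot see.

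A reader might infer three stronger things. One is that the planned summary is biased towards shorter times. The documents do not support a direction, as patterns C and D show. Another is that every infection, NPWT or refusal leaves the primary value missing. Section 4.2 covers infection at any time and refusal of the graft itself, so some of these exits can follow approval. The third is that unapproved patients are excluded from the evaluable set. Section 8.2 does not say so, and on the Synopsis list some are plausibly included.

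**Conclusion.** The point holds as a limit on interpretation that should be fixed. As written, the primary summary is conditional on approval, and the plan commits to no summary showing how many treated wounds were approved. This follows from the endpoint definition and the listed exits, and does not depend on the assumed counts.

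Its size in this trial cannot be stated. If every treated patient is approved, nothing is lost. If 4 or 10 of 20 are not, the unreported proportion is 80% or 50%, with exact intervals of 56.3–94.3 and 27.2–72.8. No error rate is involved, and a reader should not infer that days to approval is an invalid endpoint or that the collected data are compromised.

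**What to change.** Keep days to approval as the primary endpoint, labelled as among approved patients and reported with n out of all treated. Alongside it:

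- In 8.2, state which endings count as resolution of Phase I, and that all patients who received the device are the denominator for the two summaries below.
- In 8.3, prespecify the proportion approved with exact 95% intervals, after the first application and by the end of Phase I. Define both by application number, not by a hard Day 21 or Day 42 cut.
- In 8.3, tabulate every pre-approval exit by reason, with STSG no longer necessary kept apart from failures. Count patients who exit after approval as approved.

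A cumulative incidence curve with pre-approval exits as competing events is optional. It describes approval while on study and would be sparse with 20 patients.

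The cost is a few sentences, exact binomial intervals and one table. The downsides are a possibly less favourable headline and a check that the CRFs, which are separate from the protocol, record exit dates and reasons.
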